#### 7.5.9 Neurological Examinations

Incidence of any post-baseline treatment-emergent PCS neurological examinations findings as indicated on the Neurological Exam electronic CRF will be summarized for each visit (refer to Table 7-11 for analysis visit window definition) and overall during the treatment period. For overall, the record with the most severe finding will be selected for a participant. Shift tables from baseline to post-baseline will be provided.

All neurological examinations findings will be listed.

Protocol No. AL002-2 Last Revision Date: 12 Aug 2025

## 7.5.10 Physical Examinations (PE)

All PE findings will be listed.

#### 7.5.11 Other Safety Assessments

#### 7.5.11.1 Pregnancy Test

Screening reproductive status and pregnancy test results at any visit will be listed.

#### 7.5.11.2 COVID-19

Impact of COVID-19 was collected for the following: participants impacted by COVID-19, participant dispositions impacted by COVID-19, AEs, assessments, significant protocol deviation related to COVID-19, cause of impact, study drug interruption caused by COVID-19. All the COVID-19 impacted events/participants will be displayed in the by-participant data listing.

#### 7.6 Pharmacokinetic Endpoints

All PK summaries will be performed on the PK Set. AL002 concentration will be summarized by analysis visit (refer to Table 7-13 and Table 7-14 for analysis visit window definition) and nominal time point as collected, separately for serum and CSF PK. Summary statistics will include coefficient of variation (CV) as percent and geometric mean in addition to the descriptive statistics (excluding Q1 and Q3) described in Section 7.1.

AL002 mean (+ SD) concentration-time data will be plotted (linear and semi-log) by elapsed time since the first study drug administration (in hours, i.e., (time of collection – time of the first study drug administration + 1) and treatment group for the first dose, separately for serum and CSF PK. The same plot (linear and semi-log) will be repeated for the seventh dose.

AL002 mean (+ SD) trough concentration-time data will also be plotted (linear) by elapsed time since the first study drug administration (in nominal weeks) by ADA group (positive and negative), separately for serum and CSF PK. In each ADA group, all treatment groups will be combined. The ADA positive group includes all participants who had at least one positive ADA result any time post-baseline. The ADA negative group includes all participants whose ADA results were all negative post-baseline. Participants who did not have any ADA post-baseline result will be excluded from this plot.

For the summaries and mean plots of AL002 concentrations, concentrations that are below LLOQ (below the limit of quantifications (BLQs)) before the first measurable concentrations on Study Day 1 will be set to zero, and all BLQs after Study Day 1 will be set to missing. The rules specified in Section 7.1.4.1.1 do not apply to PK.

Potential correlations of serum and/or CSF PK data with demographics, safety (including QT changes), efficacy, and PD measures may be explored, as data allow. Additional modeling, including population PK analysis and/or PK/PD analyses to characterize these correlations may be performed. These additional analyses of PK/PD data will be covered in a separate analysis plan and reported separately from the CSR.

The AL002 concentration data will be listed for the ATS.

Protocol No. AL002-2 Last Revision Date: 12 Aug 2025

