- Perform/collect prior to dosing. For all post-screening MRIs, the MRI should occur at least 5 days prior to the next dose administration and no more than 10 days prior to the next dose administration, with results received from the central imaging vendor prior to dosing. Note that the central imaging vendor typically requires 5 business days after receipt of the MRI before sending a BMW to the site. MRIs may be scheduled outside of the prescribed window, with approval from the Medical Monitor. The Sponsor may request that additional unscheduled MRIs be performed for the detection and follow-up of ARIA. Participants with MRI evidence of ARIA should be managed according to instructions provided in Table 7.
- Vital signs include temperature, respiratory rate, pulse rate, and systolic and diastolic BP while the participant is at rest in a supine position for at least 3 minutes. Heart rate and BP measurements should be obtained with a validated digital monitoring device where available and an appropriately sized cuff. The same arm should be used for all BP measurements if possible. Heart rate and BP should not be measured unless 15 minutes have passed since the last blood draw.
- Perform/collect prior to dosing, and at the end of the infusion. Vital signs will be collected and concomitant medications and AEs documented prior to and at the end of infusion. Triplicate ECGs will be performed predose and 60 to 90 minutes after the end of infusion on Day 1, Weeks 5, 13, 25, and 49. On dosing visits, serum PK samples will be collected predose and within 15 minutes after the end of infusion. On the dosing visits for Day 1 and Weeks 1, 5, 9, 13, 25, and 49 serum PK samples will also be collected 60 to 90 minutes after the end of infusion. On non-dosing visits, serum PK samples may be collected at any time during the visit.
- k Urine pregnancy test (WOCBP only) and vital signs will be performed and concomitant medications and AEs will start being collected at the Predose Baseline Visit and subsequent visits for those participants participating in a Tau PET scan or Amyloid PET scan
- Assessment is to be completed only if visit is conducted for another reason (eg, COAs).

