#### 3.1.4 Treatment Administered

All participants in Part 1 and Part 2 will receive study treatment (placebo, 15 mg/kg AL002, 40 mg/kg AL002, or 60 mg/kg AL002). Study drug administration will begin on Day 1 visit and then will occur once every 4 weeks for the duration of the treatment period according to the Schedules of Assessments in the protocol.

In order to maintain the blind across all dose groups and allow step titration to the higher doses, the starting dose for each participant randomized to receive AL002 will be 15 mg/kg (or placebo) for the first study drug administration on Day 1 visit. For the second study drug administration, the dose will increase to 40 mg/kg for participants randomized to receive 40 mg/kg or 60 mg/kg, while doses in the other 2 groups will remain constant. For the third study drug administration, the dose will increase to 60 mg/kg for participants randomized to receive 60 mg/kg while doses in the other 3 groups will remain constant. The titration algorithm is provided in below Table 3-1.

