#### 7.1.1 Study Day and Visit Window Definitions

## **7.1.1.1** Study Day

The first date on which participant receives study drug (or study treatment – AL002 or placebo) per the records with non-missing dates and non-missing volume administered in the dataset corresponding to the Exposure – IV electronic CRF will be designated as **Study Day 1**. Study days for other visits will be calculated as follows:

- Before Study Day 1: Study Day = date of assessment date of Study Day 1.
- On or after Study Day 1: Study Day = date of assessment date of Study Day 1 + 1.

The **last dose date** of study drug will be the date of last dose collected on the Study Drug Completion electronic CRF or the date of last non-missing study drug administration record collected on the Exposure – IV electronic CRF, whichever occurs later.

Protocol No. AL002-2 Last Revision Date: 12 Aug 2025

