#### 7.7.1 PD Assessment Objective

#### 7.7.1.1 FAS

For exploratory PD biomarkers (CSF, plasma, amyloid PET, Tau PET and volumetric MRI) listed in Table 7-25 [subsets 1 and 2] in the FAS, their visit values, change from baseline (CFB) and percent change from baseline (PCFB) for the main estimand will be summarized by treatment group over time (all visits) using descriptive statistics (Table 7-26).

Comparisons of CFB between AL002 dose groups vs. placebo will be explored for the main estimand using MMRM models (see Section 7.4.1.2) with treatment group, categorical visit, visit-by-treatment interaction, baseline biomarker, and APOE e4 status of e4 carrier vs. non-e4 carrier as fixed effects (Table 7-26). Treatment comparisons will be reported for specified visits as indicated below:

- Plasma biomarkers:
  - O AD-pathology (Aβ42/40, pTau217, MTBR-Tau243): week 12, 24, 48, 72 and 96
  - o AD-pathology (pTau181): week 16, 36, 60 and 84
  - o Target engagement (IL1RA): week 1, 2, 4, 6, 8, 12, 24, 36, 48, 72 and 96
  - o Neurodegeneration (NfL, GfAP): week 12, 24, 48, 72 and 96
- CSF biomarkers: week 6, 48 and 72
- Amyloid PET parameters: week 48
- Tau PET parameters: week 48 and 72
- Volumetric MRI parameters: week 48, 72 and 96

Additionally, the same analysis for the main estimand described above will be repeated with the following groups in the model: AL002 15 mg/kg group, AL002 40 and 60 mg/kg combined group, and placebo group. All statistics described above from fitting the MMRM model will be reported only for the AL002 40 and 60 mg/kg combined group (or its comparison to placebo).

For Tau PET parameters [subset 1] in Table 7-25, a sensitivity analysis (main estimand) will be conducted with similar descriptive summaries and MMRM models for the subset with redefined baseline (either pre-dose Tau PET if evaluable or the first post-dose evaluable Tau PET scan if pre-dose PET scan

Protocol No. AL002-2 Last Revision Date: 12 Aug 2025

is missing) (Table 7-26). A pMMRM model (main estimand) will be additionally conducted for both subsets of true baseline and redefined baseline (Table 7-26).

Given the limited sample size mapped to the Week 96 analysis visit for CSF, Amyloid PET and Tau PET, this visit will only be summarized descriptively and excluded from modelling (i.e., pMMRM and MMRM).

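### The hour-scale PK plots in SAP 7.6 carry a stray +1 hour, give no new time origin for the seventh dose, and ask for CSF profiles where no CSF sample is scheduled

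*SAP*

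**What the plan says.** SAP 7.6 asks for mean (+ SD) concentration plots, linear and semi-log, on an axis of elapsed hours. The hours are collection time minus "time of the first study drug administration + 1) and treatment group for the first dose, separately for serum and CSF PK". The next sentence reads: "The same plot (linear and semi-log) will be repeated for the seventh dose". It gives no time origin for that second plot.

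The same section tabulates concentrations by analysis visit and nominal time point. It also plots troughs in nominal weeks, by ADA group with the treatment groups combined. Neither output uses the hour formula. Protocol 8.3.5 planned serum concentration-time displays by study day and treatment group, with CSF handled similarly when available. SAP Section 9 records no change on this point.

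**The concern.** Three things look wrong.

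- **The added 1.** SAP 7.1.1.1 adds 1 when counting study days because there is no Day 0. In hours, the same step shifts every point to the right.
- **The seventh-dose origin.** Repeating the same plot carries over the only clock that is defined, and that clock starts at dose 1.
- **The CSF versions.** Lumbar punctures are months apart and do not follow either of the two doses chosen.

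At stake are the only planned displays of concentration within a dose. A programmer who follows the text would produce a mistimed first-dose curve around the infusion, a seventh-dose figure spread by visit date, and CSF panels with next to nothing in them.

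**Working it through.** **Inputs**
- Infusion of about 60 minutes (Protocol 5.2.1).
- Serum samples: "On dosing visits, serum PK samples will be collected predose and within 15 minutes after the end of infusion" (Protocol Table 9 footnotes). Weeks 1, 5, 9, 13, 25 and 49 add one at 60 to 90 minutes after the end of infusion (Protocol 6.7).
- Optional samples at 4, 8 and 24 or 48 h after the infusion at Week 25, 37 or 49, in about 64 Part 2 participants (Protocol 6.7).
- Later serum samples after dose 1: Days 8 (Part 1 only), 15 and 29 (Protocol Tables 8 and 9).
- Dosing: "Study drug administration will begin on Day 1 visit and then will occur once every 4 weeks" (SAP 3.1.4). Dose k therefore falls on Day 1 + 28(k − 1).
- Visit window in Protocol Table 9: ±5 days.
- CSF: screening or predose baseline; Day 43 in Part 1; Weeks 49 and 73; EFU or ET if due (Protocol 3.1.10 and Tables 8 and 9). SAP Table 7-14 has Baseline and Weeks 6, 48 and 72 only. The biomarker visits in SAP 7.7.1.1 agree: "CSF biomarkers: week 6, 48 and 72".

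Administration time is taken as the start of the infusion. SAP 7.6 does not say whether it means start or end.

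**1. First dose, serum.** Plotted time = true time + 1.

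| Sample | True time (h) | Plotted time (h) |
|---|---|---|
| 30 min before dosing | −0.5 | 0.5 |
| Start of infusion | 0 | 1 |
| End of infusion | 1 | 2 |
| 15 min after end | 1.25 | 2.25 |
| 60 to 90 min after end | 2 to 2.5 | 3 to 3.5 |

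Any predose sample taken less than 1 h before the infusion appears post-dose. Relative to elapsed time, the shift is 1/1 = 100% at the end of infusion. It is 1/168 = 0.6% at Day 8, 1/336 = 0.3% at Day 15 and 1/672 = 0.15% at Day 29.

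**2. Seventh dose, serum.** Dose 7 is on Day 1 + 28 × 6 = Day 169 (nominal Week 25). On the written clock:
- The infusion starts at 168 × 24 + 1 = 4,033 h.
- A sample 30 minutes before it plots at 4,032.5 h, and the last core sample at 4,033 + 2.5 = 4,035.5 h.
- The optional 48 h sample plots at 4,033 + 49 = 4,082 h.
- The visit window is ±5 × 24 = ±120 h, a range of 240 h between participants.

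The within-dose span is about 2.5 h, or about 49 h with the optional samples. At actual times on this axis, visit date dominates time after infusion.

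**3. CSF.**
- Dose 1 interval, Days 1 to 29: no scheduled post-dose sample. Day 43 is 42 × 24 = 1,008 h after dose 1, but also 14 days after dose 2 (Day 29).
- Dose 7 interval, Days 169 to 197: no scheduled sample. The next is Week 49 (Day 337), (337 − 169) × 24 = 4,032 h later. It falls at the dose 13 visit, and Protocol 6.1 lists the lumbar puncture among predose procedures.

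**The case against.** The strongest reply is that little is harmed. A constant offset leaves curve shape, peak concentration and comparisons between doses unchanged. First-dose sampling runs to about 672 h, and with the 9.0-day half-life in Protocol 1.4 a 1 h shift corresponds to ln 2 / (9.0 × 24) = 0.3% in terminal-phase concentration. That stands. A reader might infer a 100% timing error across the serum profile, but that figure holds only at the end of infusion.

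A reader might also infer that the SAP states a first-dose clock for dose 7. It does not: the clock is only carried over by the words about repeating the plot. Moving the origin to the seventh dose is a natural reading of that shorthand. Means formed at nominal times, as in the tables of the same section, would remove the scatter. The firm criticism is that the text gives no new origin and can be programmed literally.

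A reader might call the CSF plots empty. That goes too far. Isolated points could come from unscheduled punctures after ARIA, ET visits, or missed or paused doses that move the actual seventh dose. A Part 1 participant stopped for ARIA on the Day 15 MRI could also have the Day 43 puncture after dose 1 alone. Such points would be too sparse for a mean (+ SD) profile.

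One could take the +1 as a nominal infusion hour added to an end-of-infusion time. The SAP does not say so, and Protocol 5.2.1 records both the start and the end of each infusion, so no fixed hour is needed.

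**Conclusion.** The point holds as a minor correction to descriptive figures.

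- **+1 hour:** wrong as written if administration time means the start of infusion. It is material within the first few hours and negligible at Days 8, 15 and 29.
- **Seventh-dose origin:** not specified. The values near 4,033 h and the scatter of up to ±120 h rest on the literal reading, actual sampling times, and a seventh dose given at Week 25.
- **CSF profiles:** no scheduled sample within either dosing interval, provided dosing follows the schedule.

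The documents do not support any wider conclusion. Concentration tables, trough plots, and efficacy and safety inference do not use this clock.

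**What to change.** In SAP 7.6:

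1. Delete the +1.
2. Define elapsed hours as collection time minus the start of the infusion being plotted, naming dose 1 and dose 7 (nominal Week 25) separately.
3. State that means are formed at nominal time points.
4. Replace the CSF dose 1 and dose 7 plots with CSF concentration by analysis visit (Baseline, Weeks 6, 48 and 72) and treatment group. This is close to what Protocol 8.3.5 described. It is not already covered by the CSF trough plot, which pools treatment groups by ADA status.

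Both serum plots would then share one axis: predose at or below 0 h, end of infusion at about 1 h, core samples to about 2.5 h, and optional samples at about 5, 9 and 25 or 49 h. The cost is SAP wording and plot code, with no new data.

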3.1.2. Study Objectives

The objectives of this Phase 2 study are the assessment of the efficacy and safety of IV AL002 treatment for up to 96 weeks. Multiple dose levels of AL002 will be studied against placebo at a dosing frequency of every 4 weeks. Participants with the *APOE* e4/e4 genotype who were enrolled under Versions 1–4 of this protocol will not receive any further study drug treatment, but should continue with the remaining planned visits in the Schedules of Assessments (Section 14.1).

Efficacy will be assessed with clinical outcome assessments (COAs) as well as fluid and imaging biomarker measures. Safety will be assessed through monitoring of AEs (including AESI and SAEs), changes in laboratory and vital sign values, incidence of findings from physical, neurological, ECG, MRI and ophthalmological exams, and reports of suicidal ideation or behavior. PK in both the serum and CSF will be assessed for investigation of exposure-response and exposure-safety relationships. Blood biomarker and MRI biomarker measures will be assessed for all participants.

In this study, several optional PD assessments will be performed for those participants who consent to the assessments. These include CSF collection for fluid biomarkers (except for Part 1, where CSF collection is mandatory for all visits), PET imaging with the tau radiotracer [18F]MK-6240, longitudinal Amyloid PET imaging, and/or speech assessment with the Winterlight Labs Speech Assessment (WLSA).

AL002 Alector, Inc.

3.1.3. Enrollment in Part 1 and Part 2

In Part 1, each dose level tested will consist of a minimum of 10 participants. Approximately 40 participants will be randomized at a 1:1:1:1 ratio to receive either AL002 15 mg/kg, 40 mg/kg, 60 mg/kg, or placebo, administered via IV infusion every 4 weeks. The remainder of the study will be enrolled as Part 2 which will include approximately 288 participants. The allocation ratio in Part 2 will also be 1:1:1:1. Participants randomized after July 2021 to receive 40 or 60 mg/kg will be titrated to their target randomized dose level over the first 2 or 3 doses, respectively, and then continue at their randomly assigned dose for the remainder of study participation. There will be no change to dose for participants randomized to receive 15 mg/kg or placebo.

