#### 5.2 As-Treated Set (ATS)

The ATS will consist of all participants who received any study treatment. All analyses using the ATS will group participants according to the actual treatment received.

If a participant is randomized to any dose level of AL002 and receives any amount of AL002, they will be analyzed at the highest dose level of AL002 received by the participant. Especially for participants who went on the dose titration algorithm (Table 3-1), their actual treatment received will be determined based on their Exposure – IV electronic CRF records and the participant visit dispensing history in the Interactive Response Technology (IRT) system.

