#### 5.3.4 Pharmacokinetic (PK) Set

The PK Set will include all participants in the ATS that received AL002, had at least one post-dose measurable concentration, and are non-e4/e4. The PK Set will only be used for concentration descriptive summary.

All PK summaries using the PK Set will group participants according to the actual treatment received and follow the same rules as described above in the ATS (Section 5.2).

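### First-dose and titration-period PK outputs label each participant by the highest AL002 dose ever received, not by the dose infused before the sample

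*SAP*

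**What the plan says.** SAP 7.6 tabulates AL002 concentration by analysis visit and nominal time point. It also plots mean concentration against hours since the first administration, by "treatment group for the first dose, separately for serum and CSF PK", and repeats that plot for the seventh dose. SAP 7.1 defines the treatment groups as 15, 40 and 60 mg/kg and placebo.

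The group label comes from two other sections. SAP 5.3.4 says that PK Set summaries "will group participants according to the actual treatment received and follow the same rules as described above in the ATS". SAP 5.2 says of participants who were randomized to AL002 and received any of it that "they will be analyzed at the highest dose level of AL002 received by the participant". It singles out titrated participants ("Especially for participants who went on the dose titration algorithm"), but only to name the records from which the treatment received is determined.

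On dosing, SAP 3.1.4 states that "the starting dose for each participant randomized to receive AL002 will be 15 mg/kg (or placebo) for the first study drug administration", and Table 3-1 gives the later steps. Protocol 3.1.4 and 5.2 likewise apply the 15 mg/kg start without a date limit. Protocol 3.1.3 does give one: "Participants randomized after July 2021 to receive 40 or 60 mg/kg will be titrated to their target randomized dose level". Protocol 3.3.3 repeats the July 2021 limit.

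Elapsed hours are defined in SAP 7.6 as the collection time minus the "time of the first study drug administration + 1".

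**The concern.** A label fixed at the highest dose ever received suits a summary over the whole study. It does not suit a first-dose concentration curve in a trial with step titration, where the first infusion is by design below the final dose in two of the three active arms. A curve headed 60 mg/kg would then show concentrations after 15 mg/kg. If some participants under the same label started at the full dose, the curve would average two regimens, and the coefficient of variation that SAP 7.6 reports would include the gap between them.

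At stake is the reading of a descriptive output. Someone who takes the label as the dose given could conclude that early exposure hardly rises with dose, or that it is unusually variable, when the label is the cause.

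**Working it through.** The plan states no figure to reproduce here. The check traces the label, compares it with the dose infused, and sizes the difference.

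**1. Label against dose infused, titrated participants (SAP 5.2 and Table 3-1).**

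| Label (highest dose received) | Infusion 1 | Infusion 2 | Infusion 3 |
|---|---|---|---|
| 60 mg/kg | 15 | 40 | 60 |
| 40 mg/kg (arm schedule) | 15 | 40 | 40 |
| 15 mg/kg (arm schedule) | 15 | 15 | 15 |

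Infusion 1 is 15/60 = 25% of the label for 60 mg/kg (a 4-fold gap) and 15/40 = 37.5% for 40 mg/kg (2.67-fold). Infusion 2 is 40/60 = 67% of the label for 60 mg/kg and equals the label for 40 mg/kg. A participant who stopped during titration carries the lower dose reached, so the rule does not credit that participant with a dose never given.

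**2. Mixing of regimens.** Let f be the share under a label who started at the full dose T. The documents do not give f, so a range of 0 to 50% is assumed. One illustrative value is 10/82 = 12.2%: the Part 1 minimum per dose level (Protocol 3.1.3) over the planned group size (Protocol 8.1). It supposes that exactly those 10 were untitrated and that all of them are in the PK Set; neither is stated.

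Mean nominal first dose = f·T + (1 − f)·15. Between-regimen SD = (T − 15)·√(f(1 − f)). CV = SD/mean.

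| f | 60 label: mean (mg/kg) | CV | 40 label: mean (mg/kg) | CV |
|---|---|---|---|---|
| 0 | 15.0 | 0% | 15.0 | 0% |
| 5% | 17.25 | 57% | 16.25 | 34% |
| 12.2% | 20.5 | 72% | 18.1 | 45% |
| 25% | 26.25 | 74% | 21.25 | 51% |
| 50% | 37.5 | 60% | 27.5 | 46% |

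Example at f = 12.2%, T = 60: mean = 0.122 × 60 + 0.878 × 15 = 20.5; SD = 45 × √(0.122 × 0.878) = 14.7; CV = 14.7/20.5 = 72%.

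At infusion 2 the 60 mg/kg label averages 60f + 40(1 − f), which is 40 to 50 mg/kg over the same range. These are nominal doses. They carry over to concentrations only as far as exposure is proportional to dose; Protocol 1.4 reports Cmax and AUC in Phase 1 as generally so.

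**3. Outputs reached.**
- The first-dose plot: 40 and 60 mg/kg labels.
- Visit summaries after infusion 1 up to predose Week 5 (SAP analysis visit Week 4): 40 and 60 mg/kg labels.
- Visit summaries from post-infusion Week 5 to predose Week 9 (SAP analysis visit Week 8): 60 mg/kg label only, because infusion 2 in the titrated 40 mg/kg arm is already 40 mg/kg.
- The seventh-dose plot falls after titration, and the plot by anti-drug antibody status pools all dose groups, so this labelling rule hardly touches either.

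**4. Elapsed hours.** SAP 7.1.1.1 adds 1 in the Study Day formula so that the first day is Day 1. In hours the same term moves every sample 1 hour late. If time runs from the start of a 60-minute infusion, which SAP 7.6 does not specify, a sample 15 minutes after its end belongs at 1.25 h and would be plotted at 2.25 h.

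**The case against.** The strongest reply is that a treatment group is an arm, and the 60 mg/kg arm is the regimen 15, then 40, then 60 mg/kg. A first-dose curve for that arm correctly shows that regimen's first infusion, the schedule is published in the SAP, and Protocol 8.3.5 already planned tabulation by study day and treatment group. This reduces the first part of the point to labelling, provided that each display states the infused dose. SAP 7.6 does not ask for that. It also does not answer the mixing of two starting regimens under one label.

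The phrase about the treatment group for the first dose could also be read as grouping by the dose given at that infusion. The instruction to repeat the plot for the seventh dose suggests that the phrase names the plot, and SAP 5.3.4 fixes the group. The reading is possible but weaker.

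The mixing itself is an inference. A reader might take it as established that participants randomized before the July 2021 change started at 40 or 60 mg/kg. The documents do not say so. The date limit in Protocol 3.1.3 and 3.3.3 and the wording of SAP 5.2 point that way, but Protocol 3.1.4 and 5.2 and SAP 3.1.4 give every AL002 participant a 15 mg/kg start. If those sections are literally right, there is no mixing, but the whole first-dose curve under both higher labels is then 15 mg/kg data.

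The objection that the outputs are descriptive also stands: SAP 5.3.4 confines the PK Set to descriptive concentration summaries, and SAP 7.6 sends PK modelling to a separate plan.

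**Conclusion.** The point holds as a labelling and grouping fault in descriptive PK outputs. For titrated participants, the first infusion is 25% of a 60 mg/kg label and 37.5% of a 40 mg/kg label, whatever the untitrated share. The extent of mixing is unknown: an assumed share of 0 to 50% puts the mean nominal first dose under the 60 mg/kg label anywhere from 15 to 37.5 mg/kg.

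Two stronger conclusions might be inferred and are not supported. One is that every Week 5 summary is mislabelled; the post-infusion Week 5 mismatch concerns the 60 mg/kg label only. The other is that the choice of a Phase 3 dose would be misled. Protocol 1.4 says that testing these doses will inform that choice, but does not tie it to the first-dose plot. Efficacy analyses, error control and sample size do not use this label.

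The added 1 is a separate, small error: it shifts the time axis and leaves concentrations and curve shape unchanged.

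**What to change.** In SAP 7.6, for the first-dose plot and all PK summaries before the third infusion, show titrated and untitrated participants separately within each arm. Label every curve or row with the mg/kg actually infused. The Exposure – IV and IRT records named in SAP 5.2 supply both items.

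Grouping only by the preceding infusion would be less satisfactory. At infusion 2 it pools participants who went from 15 to 40 mg/kg with those who had 40 mg/kg twice. With the 9.0-day half-life in Protocol 1.4, about 2^(−28/9.0) = 12% of the earlier concentration remains after 28 days. It would also move participants between groups within one visit and leave Day 1 predose samples without a group.

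Reconcile the passages that limit titration to participants randomized after July 2021 with those that apply the 15 mg/kg start to all AL002 participants. Delete the added 1 from the elapsed-hours formula.

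The cost is SAP wording and programming on data already held, plus a few curves with small numbers.
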